3.0 STUDY POPULATIONS

3.1 Inclusion Criteria Early HIV-1 Infection Subjects

One of the following must be fulfilled:

- Recent Infection: Documented HIV-1 antibody seroconversion within the past six months OR
- Acute Infection: HIV-1 antibody negative or indeterminate and HIV-1 PCR + or p24 antigen positive

OR

• Recent Infection: As determined by detuned ELISA (This test is expected to be available within the next year. The reliability of this test is currently under evaluation(35))

All of the following must be fulfilled:

- Willing and able to provide informed consent
- Aged > 18 years
- Willing to permit phlebotomy of four tubes of blood (40 mls) every three months for 24 months

3.2 Exclusion Criteria

- An obvious psychological/psychiatric disorder that would invalidate the informed consent process or otherwise contraindicates participation in the study.
- ♦ Hemoglobin level < 7mgs/dl

3.3 Inclusion Criteria for HIV-uninfected Controls

- HIV-antibody negative using standard site specific screening algorithm
- Self-report at low risk for HIV-1 infection for prior one year and at the time of enrollment
- Willing and able to provide informed consent
- Aged > 18 years

3.4 Exclusion Criteria for HIV-uninfected Controls

- ♦ HIV-infected
- An obvious psychological/psychiatric disorder that would invalidate the informed consent process or otherwise contraindicates participation in the study
- ♦ Hemoglobin level < 7mgs/dl

3.5 Conditions for Participant Withdrawal

- A participant may be discontinued early from the study for any of the following reasons:
- Participant withdraws consent/decides that s/he does not want to continue in the study.
- A clinician or the site PI decides that continued participation is not warranted or advisable due to health reasons or other reasons related to the well-being of the participant, including an obvious psychological/psychiatric disorder that would invalidate the informed consent process, or otherwise contraindicate participation in the study.
- Any other condition that in the opinion of the study site Principal Investigator will interfere with achieving the study objectives. The decision to withdraw the participant should be done in consultation with the Protocol Co-Chairs and HPTU 034 Core Protocol Team.
- Reasons for discontinuation from the study will be recorded on the appropriate case report form.

4.0 STUDY PROCEDURES

This section refers to clinical and laboratory procedures that will be used to evaluate outcomes for each of the primary objectives. The procedures discussed below will be used to accomplish the primary and secondary objectives in this protocol.

4.1 HIV-1 Screening

HIV-1 screening will be performed as described in section 4.4.1

4.2 Enrollment

Enrollment will take place over the two years of the HPTN 034 protocol; participants will be followed for up to two years, if funding is available. The schedule for sample collection is outlined in Table 1. If it can be determined that participants were infected within the previous three months, samples would be drawn at enrollment, once a month for three months, and then every three months for up to two years. If participants have been infected for more than three months, and less then six months, specimens would be collected at enrollment, and every three

months for up to two years. Participants will be asked to provide a 40 ml blood sample (four EDTA vacutainer tubes, 10mls/tube), answer a short questionnaire and undergo a brief physical exam. PBMC and plasma will be stored on site for immunologic and virologic studies through the CL.

Study participants with recent HIV-1 infection will be also be strongly advised to refer their primary sexual partner(s) for HIV-1 screening and risk reduction counseling. Sexual partners of participants with recent HIV-1 infection who agree to HIV-1 screening will be determined to be either chronically HIV-1 infected of unknown duration, recently HIV-1 infected themselves, or HIV-1-uninfected. Those partners found to be recently HIV-1-infected will also be eligible for enrollment in this study. Partners found not to be HIV-1 infected will be eligible to enroll in a companion HPTN sub-study of exposed-uninfected partners (HPTN 034B).

4.3 Follow-up

At each follow-up visit (seropositive subjects) the participant's identity and ID number will be verified. A physical exam and questionnaire will be completed. Specimens will be collected, processed and stored/shipped according the study-specific procedures manual and the schedule shown in Table 1 (Appendix A). The next appointment will be scheduled (if required) and the appropriate data collection forms will be completed.

To maximize efficiency, established systems for follow-up at NARI will be utilized to the extent possible, including the use of home visitors, modest incentives, and tracking procedures. If a participant misses a scheduled study visit, the study site staff will try to establish communication with the participant through all possible means using the contact information provided by the volunteer. The need to adhere to the visit schedule will be emphasized at each contact. Participants may be compensated for meals, time away from work and for transportation to the study clinic as appropriate.

4.4 Laboratory Assays

4.4.1 Diagnosis of HIV Infection:

As outlined in the 034 protocol we will utilize commercially available HIV antibody assay kits for HIV screening. To be documented as HIV infected for the purposes of this protocol, eligible subjects must have a current positive HIV antibody test and a negative HIV antibody test result within the prior 6 months. A positive antibody test would be defined as either A) HIV + by two different rapid tests B) HIV+ by two different serum ELISA tests C) HIV+ by one rapid AND one serum ELISA test or D) HIV+ by either a rapid test OR an ELISA AND by one HIV western blot. As outlined above, individuals who are NOT HIV antibody positive, based upon any of the above four criteria, may also be enrolled in this study if they are identified in the pre-antibody seroconversion "window".

4.4.2 HIV-1 Viral Load Testing:

The Pune HPTU site will be expected to perform HIV-1 PCR and viral load (VL) measurements for studies outlined in this protocol, as well as other potential HPTN protocols such as preparedness studies, perinatal studies, and ART protocols requiring VL measurements. The HCL will recommend the use of the Roche Amplicor HIV-1 Monitor[™] Test version 1.5 because of its increased sensitivity and ability to detect non Clade B subtypes of HIV-1 (36). This assay would be recommended for sites interested in screening HIV-1 antibody negative specimens for identification of HIV-1 PCR+ subjects in the "window" period for enrollment in this protocol. This same assay would be utilized on-site for all VL assays for study participants. The HCL virology core will provide training for this HIV-1 PCR assay. This assay contains quality control material in the form of negative, low and high standards that will be used with each assay run. There is also an internal standard control that is assayed with each specimen. NARI will also be required to participate in QA proficiency testing on a quarterly or semi-annual basis through a DAIDS-sponsored Virology Quality Assurance (VQA) program already in place in the US. More detailed information on the viral load assay is provided in Appendix C.

4.4.3 Specimen Processing and Storage

The HCL immunology group will provide training and technical support to the PUNE site in a number of laboratory techniques required for this protocol, including collection, processing and storage of patient specimens, as well as a the immunological assays required for this study. Initially, the HCL will focus on training and providing quality control assessments of the NARI HPTU in specimen collection and storage procedures. Proper specimen processing and storage is essential, prior to performing the immunological assays proposed for this study. This initial training can be performed using seronegative volunteer samples, to avoid using more limited seropositive samples. Therefore, for this purpose, NARI will be expected to enroll 20 seronegative volunteers at the on-set of the study, and then up to 10 seronegative volunteers for each year of the study.

The HIV-1 negative control samples will be used for:

- Quality controls for freeze/thaw and viability protocols
- HLA screening for population genetics
- Negative controls in future immunologic assays

The Pune HPTU must meet or exceed guidelines that will be outlined in the study-specific procedures manual for cell preparation and preservation quality (Appendix D). While it is clearly optimal to use freshly isolated PBMC for real-time assays, it is likely that in this study, and in future larger HIV-1 prevention and vaccine studies, the use of frozen specimens will be necessary for batch testing. It has been previously shown that cryopreserved PBMC can be used for detection of cellular immune responses in HIV-1-infected volunteers (28;37). The NARI site will be required to periodically perform quality control analysis of frozen cells by thawing single aliquots of cells from negative controls to assess cell number and viability (detailed in studyspecific procedures manual). For example, it would be expected that NARI would be able to recover 50% or greater of the total number of PBMC stored, and that the viability of thawed cells would be approximately 90%. This number is based on previously observed recoveries from cryopreserved PBMC from HIV-1-infected individuals (38;39) Additionally, sites with flow cytometry capacities will be able to do more sophisticated measurements of cell preservation by testing for cell surface marker integrity. It has been previously shown that, cryopreservation of cells does not significantly alter the cell surface expression of most lymphocyte markers studied (40).

4.4.4 HLA typing

PBMC from HIV-1 uninfected individuals will also be used for HLA typing to be performed in collaboration with [name] Laboratory at The University of New Mexico Health Science Center Albuquerque, New Mexico. NARI would be required to ship a single frozen vial of PBMC to this laboratory for HLA typing. There is increasing evidence that HLA type influences the course of a number of diseases such as HIV-1 and malaria (41;42). Furthermore, identification of CTL epitope specificities using HLA types for modeling binding motifs has

become a standard practice in cellular immunology. Therefore, characterizing the HLA types of the populations within the HPTN will be important in understanding risk of HIV-1 infection and the immune response subsequent to infection.

4.4.5 ELISPOT Assays

As mentioned above, NARI will be evaluated for their ability to collect and store blood specimens. Once NARI is able to adhere to the quality control requirements outlined above and in the site-specific study manual (Appendix D), they will be encouraged to participate training workshops at Johns Hopkins University as well as on-site and regionalized HPTN training. Training will be provided for participation in future virologic and immunologic studies of acute seroconvertors including measurements of T cell function through ELISPOT and flow cytometry analysis (where available). If procedural problems or inconsistencies occur in QC procedures, NARI will be responsible for internal problem solving, however, communication with the HCL group will be encouraged. Personnel from the HCL will periodically visit NARI for technical support and site evaluation.

NARI would be requested to identify at lease two key personnel on site as responsible for supervision and implementation of the study protocols. The site PI should be one of the site contacts, and the other should be a key laboratory scientist directly involved in the processing and laboratory testing of specimens. Representatives of NARI would be invited to join the Protocol Team to contribute to the design of the subsequent immunologic and virologic studies to be undertaken with the specimens in the site repositories. The HPTN Immunology Group will also invite and encourage participation and collaboration with investigators outside of the HPTN for future studies.

The ELISPOT assay is an alternative functional assay that can measure $CD8^+T$ cell function. The read-out of the ELISPOT assay is secretion of IFN- γ from HIV-1-specific T cells. Secreted IFN- γ is captured onto a membrane-coated ELISA plate by an IFN- γ -specific monoclonal antibody. It is then detected using a second biotinylated IFN- γ -specific monoclonal antibody, and developed using standard ELISA reagents. The number of spots counted in a particular sample well corresponds to the number of HIV-1-specific T cells in the well/total number of cells added. Therefore, the relative frequency of cells that are specific for a particular antigen can be determined. This assay can also measure a positive and negative response for each sample tested. The positive control consists of the addition of PHA to replicates of PBMC samples. A majority of CD3⁺ lymphocytes will secrete IFN- γ in response to this mitogen. The negative controls for this assay are mock-stimulated replicates in which no stimulus is added. This allows for the assessment of background levels of IFN- γ secretion. For purposes of quality assurance, the HCL will create a panel of frozen PBMC to serve as positive and negative control samples. These cells will be distributed to each participating HPTU site to test in a blinded fashion in the ELISPOT assay using a standard set of reagents.

An important issue for the ELISPOT assay is the choice of HIV-1-antigens to use for the *in vitro* stimulation. The use of overlapping pools of HIV-1 gag peptides for *in vitro* stimulation has been shown to be an effective means of characterizing the gag-specific immune response to HIV-1 in acute and chronic infection (34;43-47). One complicating factor that will need to be addressed is whether to use sequence-specific HIV-1 antigens for the *in vitro* stimulation. Designing peptides that match the predominant transmitting strain of HIV-1 in the transmitting population in Pune would be extremely difficult and expensive. Furthermore, because there is limited data on the importance of customizing overlapping peptide sequences to match subtypes of HIV-1 represented at each site, it is not clear that this would outweigh the substantial cost of synthesizing multiple sets of peptides. Therefore, the HCL will attempt to provide reagents that are based on the best information currently available on viral subtype amino acid sequences. These sequences will be obtained from sequencing data from the sites themselves, sequences published in the current literature, and the compendium of sequence data from the HIV-1 molecular database at the Los Alamos National Laboratory (49).

Based upon the data from prior studies and an assessment of the logistical limitations of initiating this study, this proposal will initially focus on measurement of HIV-1 gag-specific ELISPOT responses utilizing a matrix format of pools of overlapping HIV-1 gag peptides (24-26;50). NARI will initially be provided with a set of HIV-1 subtype C gag peptides. Based upon this initial analysis of the gag-specific responses and upon data from other ongoing studies, we propose to consider expanding this analysis to include assessment of other HIV-1 antigens, including env, pol, nef and tat. The details of the proposed consensus ELISPOT assay with gag peptides are provided in Appendix D.

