6.3 Statistical Considerations and Sample Size Calculations

Based upon assumptions outlined below for each of the two primary objectives, the target samples size for this study is a minimum of 20 subjects with recent HIV-1-infection retained for at least 1 year of follow-up. For both primary objectives, HIV-1 viral set point will be an outcome measure. Subjects will be stratified according to median viral load measured between 6 and 12 months after estimated time of primary infection (See Table 1. viral set point=median VL

of visits 5-8). Based upon this calculation, subjects would be stratified into the following categories: <10000 copies/ml, 10000-75000 copies/ml, >75000 copies/ml.

6.3.1 Primary Objective (a).

Gag-specific ELISPOT Response vs. HIV-1 Viral Set Point.

For the purposes of comparing ELISPOT response to viral load set point, gag-specific ELISPOT responses will be stratified into two categories: Responses recognizing two or fewer HIV-1 gag peptides and those responses recognizing more than two different HIV-1 gag peptides. As outlined in Appendix E, all experiments will be performed in duplicate wells. The IFN- γ -expressing spots will be calculated as the number of spots per 100,000 stimulated PBMCs. Results will be expressed as net peptide-specific IFN- γ spots / 10⁵ PBMC. A positive peptide-specific response (responders) will be defined as a mean of greater than 5 spots above the mean spots of the mock-stimulated PBMC. Study participants will be expected to have multiple ELISPOT assays within the first 12 months of follow-up (See Appendix A).

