This is a descriptive sub-study proposed for HPTN 034. Therefore, it is not expected that we will have sufficient sample size to definitively address the primary endpoint. Never the less, we will undertake the analysis as outlined on our projected sample size of 20-30 individuals. However, we have also projected that data from this sub-study would also be available for combining with similar data from other HPTN protocols in the future. Our subsequent "meta-analysis" will compare HIV-1 viral set point with the recognition of more than two (>2) gag peptides at any time point within 12 months since estimated time of infection. Separate and similar analyses will be performed for recognition of HIV-1 subtype B gag and non-B gag peptides. Additional analyses will determine if other ELISPOT outcome measures, such as consistent recognition of more than 2 gag peptides at multiple time points, also correlate with viral set point. We predict a 30% difference between the groups with respect to the proportion of individuals who elicit a broad immunologic response (defined above). With a sample size of n=39 per arm from multiple HPTN protocols in the future, we will have 80% power to detect a 30% difference (p=0.05).

Percent ELISPOT response to >2 HIV-1 gag peptides			Estimated Sa	mple Size
<10000 RNA	10000-75000 RNA	>75000 RNA	N per arm	Total N
copies/ml	copies/ml	copies/ml		
70%	50%	30%	93	279
80%	50%	20%	39	117
90%	50%	10%	20	60

Sample Size Estimate

6.3.2 Primary Objective (b).

HLA Class I alleles vs. HIV-1 Viral Set Point.

A similar "meta analysis" of data from 034A and other similar sub-studies is anticipated for this objective. The proportion of individuals with specific HLA Class I alleles will be compared with the viral load set point. Using HLA A2 as an example (known to be associated with a frequently measurable immune response to gag peptides), we posit that a higher percentage of individuals with this allele will fall into the low viral set point category. Again, we will have an 80% power to detect a 30% difference in the proportion of individuals with HLA A2 given a sample size of 39 individuals per arm.

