- Pipet out an appropriate amount of stable DAB into a conical tube and let stand at room temperature (100µl/ well; 10mls/plate).
- Wash the plates 4x in PBS-T. Add 100µl / well of stable DAB /well and incubate for no more than 2 minutes.
- At 2 minutes, discard the Stable DAB from the wells and quickly 1dd 100µl/well of tap to stop the reaction. Discard. Rinse plate under running tap water several times to prevent over-development.
- Count the spots with a stereomicroscope (Stemi 2000 stereo microscope, Carl Zeiss, Inc. New York) under magnifications of 20-40x.
- 11. Only spots with a fuzzy border and a brown color are to be counted. (A positive test is 5 spot forming colonies per 10⁵ cells after deducting the control).
- 12. After counting, peel off the plastic backing on the plate and stick a sheet of Elisa plate sealer onto the membranes. Using a filter, punch out each well individually to insure that the membrane does not break when it is transferred to the sticky plate sealer. Either place the plate sealer cover back onto the plate sealer or store in a page protector until transport to the core laboratory for computer counting.

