The association of HIV-1 -specific CTL with non-progressive disease in HIV-1 infected persons, as well as the increased frequency of certain HLA class I alleles in HEPS populations, has led several groups to look for HLA class I restricted, HIV-1 -specific CTL in these groups(17-24). HIV-1 -specific CTL have now been described in the peripheral blood of HEPS (16). Studies by several investigators have shown that HIV-1 -specific CD8⁺ T cells can be detected in the peripheral blood of 30-60% of HEPS tested. These CD8⁺ responses have been measured both in conventional CTL lysis assays (20) as well as IFN- γ ELISPOT assays (21). Responses to multiple HIV-1 antigens were detected including env, gag, pol and nef. Interestingly, HIV-1 -specific CTL have recently been demonstrated in the genital tract, the

likely site of viral exposure, in a subset of a HEPS cohort in Nairobi (21). It has been hypothesized that a primed CTL response at the site of exposure would be more relevant in protection against incident HIV-1 infection than in blood, where HEPS CTL responses have been previously described (21). These CD8⁺ cells were most likely intraepithelial memory T lymphocytes generated in secondary lymphoid organs that localize to epithelial sites upon reexposure to antigen (25). Overall, these responses (both mucosal and peripheral) tended to be lower and not as durable as those seen in seropositive individuals. Nonetheless, the detection of HIV-1 -specific CTL in the genital tract of these HEPS suggests that these responses may be important in mediating protective immunity against heterosexual HIV-1 acquisition.

Resistance to infection with HIV-1 based on a noncytolytic CD8⁺ T cell-mediated mechanism has also been reported. Stranford et al described a CD8⁺-mediated, noncytolytic anti-HIV-1 activity that was seen in the vast majority of individuals most recently exposed to the virus (within 1 year), and was potent enough to inhibit *in vitro* infection of subject's PBMC (26). Paxton et al, showed that resistance to infection of CD4⁺ lymphocytes from HEPS was associated with the activity of C-C chemokines such as RANTES, MIP1 α , and MIP-1 β (27-29). Other HIV-1 -specific immune responses have also been observed in HEPS cohorts such as IgA in mucosa (30) (31;32)and serum (33), and serum antibodies to HLA molecules (34;35) and CD4 (36). The contribution of these mechanisms to resistance to HIV-1 infection remains unclear.

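### Participant ELISPOT plates in 034A and 034B are read by eye with no stated masking, and the plan does not say whether the eye count or the planned core-laboratory computer count decides who is a responder

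*Supplement*

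**What the plan says.** ELISPOT response is a primary endpoint in 034A (5.1.3) and in 034B (5.1.3). Section 6.3.1 of each sub-study scores duplicate wells, and a positive peptide response is "defined as a mean of greater than 5 spots above the mean spots of the mock-stimulated PBMC". 034A then splits people at more than two gag peptides. 034B counts a positive response to any gag peptide. Both accept a response at any time within a 12-month window.

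The assay instructions (034A Appendix D, repeated at the end of 034B) have the plates counted under a stereomicroscope: "Only spots with a fuzzy border and a brown color are to be counted". The same step gives the cut-off as 5 net spots, not more than 5. The membranes are then stored "until transport to the core laboratory for computer counting".

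The Pune site runs the ELISPOT assay and also the viral loads: "This same assay would be utilized on-site for all VL assays for study participants" (034A 4.4.2). In 034B it also runs the HIV tests, which Table 1 schedules at every visit. Both sub-studies regard batch testing of frozen cells as likely (034A 4.4.3, 034B 4.3.3).

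Blinding appears once in each sub-study, for the core laboratory's panel of control PBMC: "distributed to each participating HPTU site to test in a blinded fashion in the ELISPOT assay" (034A 4.4.5). No section masks the reader of participants' plates to viral load, HIV status or well type. No section says whether the eye count or the computer count is scored, or how a disagreement is settled.

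**The concern.** The spot count is the exposure variable, and both hypotheses have a direction: broader recognition goes with a lower set point (034A), and a detectable response goes with less infection (034B). Deciding whether a spot has a fuzzy border is a judgement. If the reader can learn the participant's viral load or later infection status, and can see which wells are mock, doubtful spots can be resolved towards the hypothesis. That would create an association that is not there.

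034B is probably the more exposed of the two. One positive peptide is enough, and its Background (1.1) says responses in exposed-uninfected people "tended to be lower and not as durable as those seen in seropositive individuals", so more wells may lie near the cut-off. An objective count is already planned but has been given no role in the analysis.

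**Working it through.** **1. The plan's own figure.** For 034A, pooled-variance formula, two-sided 0.05 (sidedness is not stated; two-sided reproduces the table):

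n = [1.96·√(2p̄q̄) + 0.8416·√(p₁q₁ + p₂q₂)]² / (p₁ − p₂)²

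With 80% vs 50%, p̄ = 0.65: (1.96·√0.455 + 0.8416·√0.41)² / 0.09 = (1.322 + 0.539)² / 0.09 = 38.5, so 39 per arm, as stated (power 80.5%). The other rows, 93 and 20, also reproduce. No sample-size figure is in dispute.

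**2. How one spot moves a peptide.** From 6.3.1: two stimulated wells, two mock wells, positive if the difference in means exceeds 5. Assumed, because the documents give no spot levels: Poisson counts, mock mean b = 1 to 3 per well, true net mean s.

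- D = (sum of two stimulated wells) − (sum of two mock wells), distributed Skellam(2(s + b), 2b).
- Correct reading: positive if D > 10.
- Stimulated wells read one spot high: D rises by 2, so positive if the true D > 8. One spot low: positive if D > 12.
- All four wells read one spot high: +2 − 2 = 0, so the shift cancels exactly.

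At s = 5, p for one peptide is 0.434 (b = 1) to 0.451 (b = 3). Read high it is 0.646 to 0.621, and read low 0.245 to 0.292.

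**3. Person level, 034A.** Assume five reactive peptides and one visit: P(more than two) = 10p³q² + 5p⁴q + p⁵. Ranges are over b = 1 to 3.

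| True net mean | Correct | +1 per stimulated well | −1 per stimulated well |
|---|---|---|---|
| 2 | 0.0-0.1% | 0.2-1.8% | about 0% |
| 4 | 8-14% | 37-41% | 1-3% |
| 5 | 38-41% | 72-76% | 10-15% |
| 8 | 97-99% | over 99% | 89-93% |
| 10 | over 99.9% | over 99.9% | 99.4-99.8% |

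**4. Person level, 034B.** Any peptide counts. With one reactive peptide, s = 4 and b = 2: 26% becomes 44% (high) or 13% (low).

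**5. The cut-off wording.** At s = 5 and b = 2, reading the rule as at least 5 instead of more than 5 moves one peptide from 0.44 to 0.54.

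**6. Effect on the 034A comparison at 39 per arm.** The misread fractions are illustrative.

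- Reading tied to viral load, true 50% vs 50%: 10% of non-responders read up in one group gives 55% vs 50% and type I error of 7.2%. If 10% of responders are also read down in the other group, it is 55% vs 45% and 14.2%. At 20% the figures are 14.3% and 42.2%.
- Reading not tied to viral load, true 80% vs 50%: 10% of non-responders read up in both groups gives 82% vs 55%, power of 73.7%, and 46 per arm needed.

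**The case against.** Several points on the other side carry weight.

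- **Count of record.** It is tempting to infer that the plan has chosen the eye count. It has not. The cut-off sits in the same step as the eye count, but no text says which count is scored. The gap is an unstated choice.
- **Knowledge of outcome.** It is also tempting to infer that readers know viral load or infection status when they read. The documents show only that they could. Fresh cells are called optimal, batch testing is only likely, and a shared site does not mean a shared reader. The 034A set point covers months 6 to 12, so it does not exist when an early plate is read in real time.
- **A habit of one spot.** A habit common to all wells cancels. Harm needs peptide wells to be treated differently from mock wells.
- **The model.** The assay uses a matrix of peptide pools, so five independent peptide wells is a simplification. Initial positives also get further epitope work, although no text says this revises the score.
- **Status of the text.** 034A Appendix D declares itself not the final manual (the 034B copy carries no such notice). 034A calls itself descriptive, with 20 to 30 people.

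These narrow the concern but do not remove it. Coded IDs protect confidentiality, and no separate code is described that would unlink a person's cells from their viral load. The scoring rule is in 6.3.1, which is protocol text and not the draft appendix. 034A data are meant for later pooling ("With a sample size of n=39 per arm from multiple HPTN protocols in the future"), and pooling does not remove a bias that the sites share.

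**Conclusion.** The point holds as a gap that leaves a route for bias, not as evidence that bias will occur. A primary endpoint in both sub-studies rests on a visual judgement with no stated masking, and the count that decides responder status is not named.

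The size depends on assumed spot levels. Near the cut-off, one spot per stimulated well roughly doubles, or cuts to between a quarter and about two fifths, the chance of being classed as a responder in 034A at net 5. Weak (net 2) and strong (net 10) responses hardly move. A false association needs reading that follows viral load or infection status; reading that ignores them mainly costs power. The incidence and retention endpoints of the main HPTN 034 study are unaffected, and the 39 per arm stands if responder status is read without bias. The change is worth making because it is cheap and the objective count is already planned.

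**What to change.** - In 6.3.1 of both sub-studies, name the core-laboratory computer count as the value scored against the cut-off. It should be made under a code not linked to viral load, HIV status, partner or well type (mock or peptide).
- Keep the site's eye count as a quality check, made on coded aliquots so that the reader is masked to the same items. Report agreement between the two counts and state what happens when they disagree.
- Reconcile the two cut-off statements, more than 5 in 6.3.1 and 5 in the assay instructions, into one rule.

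The cost is wording, coding of aliquots and plates, and a key held away from the readers. Membrane transport and computer counting are already planned. The sample size does not change. The downside is that scored results wait for the core laboratory. That sits in some tension with the stated aim of moving these measurements on site (Rationale, 1.2, of both sub-studies), though site reading would continue for training and quality control.
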